5. Patients entered into the study will undergo a ^{11}C -choline PET CT scan and MRI scan. The CT scan will be performed with intravenous contrast unless deemed unsafe by lab values. The CT and MRI images will be evaluated for evidence of metastatic prostate cancer. The ^{11}C -choline PET CT and MRI images will be evaluated for evidence of metastatic prostate cancer. Unequivocal evidence of metastasis on both conventional imaging and ^{11}C -choline PET will be considered a true positive. Evidence of metastasis on conventional imaging or ^{11}C -choline PET will be confirmed with biopsy or surgical pathology when possible, or by response to treatment on subsequent imaging. If confirmation of metastasis is not achievable by biopsy or surgical pathology, then confirmation will be achieved with ^{11}C -choline PET CT and MRI images obtained 3 months after treatment conclusion. Rates of confirmed metastasis between conventional CT and MRI images will be compared with the ^{11}C -choline PET CT and MRI images.
6. Upon conclusion of each imaging protocol, the referring physician will receive written documentation of the results. At this time, the patient will be considered off study and no further follow up is required.

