5.4 Imaging Review and Interpretations

5.4.1 Image Review

There will be two aspects to the evaluation, interpretation and use of the imaging data that is produced as part of this study. First, the information will be used immediately by the primary treatment physician to best assess the patient's status and select a therapy regimen. Second, at the end of the study, all of the patient data will be gathered for a comprehensive review which will proceed as follows:

1. Each patient will be assigned a research participant number at the time of consent.
2. This participant number will be substituted for all patient identifying information, where possible.
3. Any remaining patient identification information will be scrubbed from the patient files.
4. The patient identifier key will be stored on a password protected computer at DMH.
5. Access to this identifier key will be restricted from any of the data reviewers.
6. Scrubbed patient images with the identifier will be saved to a compact disc for radiologist review.
7. Studies will be presented in a random order for analysis.

8. The imaging studies will be interpreted by board certified radiologists:
 - a. Dr. [name]
 - b. Dr. [name]
 - c. Dr. [name]
9. Worksheets will be saved in a locked cabinet at DMH. The worksheets will be scanned and added to the secure computer study database.
10. The imaging reviews will be compared to the histological data or post-treatment imaging data for statistical analysis.

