6.2 Warnings and Precautions

- Imaging errors have been reported during previous clinical studies with ^{11}C -choline PET and PET/CT imaging. A negative image does not rule out the presence of recurrent prostate cancer and a positive image does not confirm the presence of recurrent cancer. ^{11}C -choline uptake is not specific

Investigatory New Drug
**Clinical Trial Protocol:
Choline C11 Injection**

Revision Date: _01/30/2015

Page 20 of 59

for prostate cancer and may occur with other types of cancer, such as lung carcinoma and brain tumors.

- Blood PSA levels < 2 ng/mL have been associated with poor performance ^{11}C -choline PET imaging, with indications of higher numbers of false positive and false negative results.
- Tissue inflammation as well as prostatic hyperplasia have been associated with false positive ^{11}C -choline PET images.
- Concomitant colchicine or androgen-deprivation therapeutic drugs, such as luteinizing hormone-releasing analogs and anti-androgen drugs, may interfere with ^{11}C -choline PET imaging. One published report of ^{18}F methylcholine PET imaging indicated that discontinuation of colchicine for two weeks resolved the colchicine effect. The impact of discontinuation of androgen-deprivations therapy upon ^{11}C -choline PET imaging has not been established.

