6.3 Limitation of Use

^{11}C -choline PET imaging is NOT a replacement for histologic verification of relapsed prostate cancer.

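### Without pathology, a repeat choline PET can confirm a choline-PET lesion, so the index test is part of its own reference standard; the net direction of the bias cannot be determined

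*Combined protocol and SAP*

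**What the plan says.** All references are to the comparison protocol, the first of the two protocols in the combined document. The expanded-access protocol that follows plans no analysis.

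- **Section 5.1, item 5, usual route.** Evidence of metastasis on conventional imaging or choline PET "will be confirmed with biopsy or surgical pathology when possible, or by response to treatment on subsequent imaging".
- **Section 5.1, item 5, fallback.** "If confirmation of metastasis is not achievable by biopsy or surgical pathology, then confirmation will be achieved with" choline PET CT and MRI "images obtained 3 months after treatment conclusion".
- **Section 5.1, item 5, agreement rule.** "Unequivocal evidence of metastasis on both conventional imaging and" choline PET counts as a true positive, with no outside check.
- **Section 5.4.1, item 10.** "The imaging reviews will be compared to the histological data or post-treatment imaging data for statistical analysis".
- **Section 5.5, Data Analysis, items 1 and 3.** A positive image backed by pathology or by response to treatment, including androgen suppression, is a true positive. A positive image without either is a false positive. Both rules cover conventional and PET images.
- **Section 5.1, item 6.** Once the result has gone to the referring physician: "At this time, the patient will be considered off study and no further follow up is required".

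Response is not defined, and nothing says which component of the repeat session (uptake, CT or MRI) decides it.

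**The concern.** A reference standard should not contain the test it judges. Under the fallback, choline PET calls a lesion positive and a later choline PET can help certify that call.

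The protocol's own cautions make this more than a formality. Section 6.3 states that choline "PET imaging is NOT a replacement for histologic verification of relapsed prostate cancer". Section 6.2 says that a positive image does not establish recurrence, that "Tissue inflammation as well as prostatic hyperplasia have been associated with false positive" choline PET images, and that androgen-deprivation drugs may interfere with the scan. Yet response to androgen suppression is one of the confirmations accepted in section 5.5. Uptake could therefore fall after treatment although no metastasis was ever present.

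The exposure is greatest for lesions called on uptake alone. Section 5.4.2 lets PET call a lymph node of any size positive on uptake, while the CT rule needs more than 1 cm in short axis. For a smaller node with no other abnormality, the change in uptake may be the only evidence of response.

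Objectives B and E, and the comparison of confirmed-metastasis rates with conventional imaging, rest on this classification.

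**Working it through.** The plan gives no figure for how positives will be verified. Its 66 pairs use no verification input and are not in question here. The check is an illustration per 100 men, treating each man as one finding.

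**Inputs from section 1.2.1 (the cited retrospective review of 176 patients).** Sensitivity 93%, specificity 76%, PPV 91%, NPV 81%; pathology confirmation 41.4%.

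**Step 1: the underlying table.** Prevalence solves PPV = 0.93p / (0.93p + 0.24(1 − p)) = 0.91:

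p = (0.91 × 0.24) / (0.91 × 0.24 + 0.93 × 0.09) = 0.2184 / 0.3021 = 0.723

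Per 100 men: TP 67.23, FN 5.06, FP 6.65, TN 21.06, with 73.88 positives. Check: NPV = 21.06 / 26.12 = 80.6%, against the cited 81%.

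**Step 2: the fallback route.** Three quantities are assumed:

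- u = 0.586 (that is, 1 − 0.414), the share of positives without pathology;
- c, the share of false-positive findings on this route that the repeat imaging wrongly confirms;
- r, the share of true metastases on this route that it confirms.

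The documents give neither c nor r. FN and TN are held fixed.

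- Apparent TP = 67.23 × [1 − u(1 − r)] + 6.65 × u × c
- Apparent FP = 73.88 − apparent TP
- Apparent PPV = apparent TP / 73.88
- Apparent specificity = 21.06 / (21.06 + apparent FP)

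| r | c | Apparent PPV (true 91.0%) | Apparent specificity (true 76.0%) |
|---|---|---|---|
| 1 | 0.25 | 92.3% | 78.8% |
| 1 | 0.50 | 93.6% | 81.7% |
| 1 | 0.75 | 95.0% | 85.0% |
| 1 | 1 | 96.3% | 88.4% |
| 0.95 | 0.50 | 91.0% | 75.9% |
| 0.90 | 1 | 90.9% | 75.9% |
| 0.80 | 0.20 | 81.4% | 60.5% |

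Worked row (r = 1, c = 0.50): 6.65 × 0.586 × 0.5 = 1.95 false positives become true positives. PPV = (67.23 + 1.95) / 73.88 = 93.6%. Specificity = 21.06 / (21.06 + 6.65 − 1.95) = 81.7%.

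**Step 3: where inflation stops.** Gains and losses balance when 67.23(1 − r) = 6.65c, so 1 − r = 0.0989c. For c = 0.25, 0.50 and 0.75 the break-even is 2.5%, 4.9% and 7.4% of the true metastases on this route unconfirmed. Even at c = 1 it is 9.9%.

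**Step 4: sensitivity.** This route barely moves it: 90.4% to 93.4% over r from 0.5 to 1 and c from 0 to 1.

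**The case against.** Three stronger readings are tempting, and the documents do not support them.

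- **A reader might infer that PET is simply its own reference standard.** It is only part of it. Pathology ranks first, and the fallback session is post-treatment and includes CT and MRI.
- **A reader might infer that the route serves PET calls only.** Item 5 and section 5.5 apply confirmation to conventional findings as well, and a lesion seen only on CT or MRI can change on those components. Section 5.4.2 also records diffusion-weighted MRI positivity separately from size and uptake, so a small node is not necessarily visible on PET alone.
- **A reader might infer that PET accuracy is inflated.** Section 5.5, item 3 makes every unconfirmed positive a false positive, and Step 3 shows that a modest shortfall in confirmation cancels the gain. The off-study statement in item 6 makes such a shortfall plausible.

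The inputs are also open to criticism. The 41.4% describes how true-positive scans were confirmed in the cited review, so applying 58.6% to false positives is an assumption. The rule on agreement between PET and conventional imaging takes some patients off the fallback route. Section 6.3 is a usage warning, so the conflict is a tension rather than a flat contradiction.

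All of this stands and limits the claim. It does not remove the defect: choline PET contributes to confirmation, the deciding component is unspecified, and no section requires follow-up to be judged without uptake.

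**Conclusion.** The point holds as incorporation bias of unknown net direction. When pathology is missing, sections 5.1 (item 5) and 5.4.1 (item 10) make choline PET part of the standard against which choline PET is judged.

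False confirmation favours PET: specificity would read 79–85% instead of 76%, and PPV 92–95% instead of 91%. This rests on three assumptions: 58.6% without pathology, 25–75% of false uptake resolving, and all true metastases confirmed. If only 80% of the true and 20% of the false findings on this route are confirmed, specificity reads about 61% and PPV about 81%. The documents do not say which case is nearer, so the planned estimates cannot be interpreted without knowing how each positive was confirmed.

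**What to change.** In section 5.1, item 5 and section 5.5, Data Analysis, items 1 and 3, before the study reads begin:

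1. State that a change in choline uptake alone does not make a true positive.
2. Record one confirmation type for each positive: pathology; change on CT or MRI; change in choline uptake only; agreement of PET and conventional imaging only.
3. Class uptake-only lesions as not independently confirmed, instead of silently counting them as true or false.
4. Report sensitivity, specificity, PPV and NPV for PET and for conventional imaging by confirmation type. Include a pathology-verified-only table, and tables with and without the uptake-only lesions.
5. Reconcile the post-treatment scan in item 5 with the off-study statement in item 6.

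Making stand-alone CT and MRI the sole arbiter is not advised: it would put the comparator into the reference standard. Only dropping the uptake-only lesions would add selective verification, hence both tables.

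The cost is protocol wording, one extra recorded field and extra tabulation; item 5 may cost more if the later scans are not currently secured. Restricted tables are less precise. If 41.4% of 73.9 positives have pathology (30.6), the approximate 95% half-width for a PPV of 91% grows from 1.96 × √(0.91 × 0.09 / 73.9) = 6.5 points to 1.96 × √(0.91 × 0.09 / 30.6) = 10.1 points. The PET figures may also look less favourable.

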5.5 Study Data – Statistical Analysis

- Sample Size:

This study is designed to compare fused ¹¹C-choline PET/CT and MRI scans against a standard CT scan and MRI scan. Based on the literature, the group detection rates are approximately 50%. In this study a 20 percentage point increase (eg: from 15 – 35 percent) in detection rate is the desired goal. The study is a paired design, in that each procedure will be performed on each individual. The important performance characteristics of these tests, including sensitivity, specificity, positive predictive value, and negative predictive value will be examined within this study. A sample size estimate was derived using a p-value of 0.05, a power of 80 %, and a paired chi square test for proportions. It was further assumed that the false positive rate is about 4 % and the false negative rate is about 20 %, which are similar to the literature. This would indicate approximately 66 pairs of data. To compare, an independent chi square test would indicate about 71 subjects per group for a comparable 20 point change. Increasing the sample size by 10 percent, for attrition, would increase the number of paired samples to about 73. Increasing the number of pairs to 100 will provide some flexibility on the false positive and false negative rates.

While more than 100 patients may be admitted into the study under expanded access, for the purposes of the comparison study and resulting data analysis, only the first 100 qualified patients will be admitted into the study and included in the study data.

- Data Analysis:

1. True positives will consist of evidence of metastatic prostate cancer on conventional CT or MRI images or on ¹¹C-choline PET/CT or MRI images confirmed with biopsy, surgical

pathology, or by response to treatment with androgen suppression or other medical or radiation therapy.

2. True negatives will consist of negative images.
3. False positive will consist of evidence of metastatic prostate cancer on conventional CT or MRI images or on ^{11}C -choline PET/CT or MRI images, but without corresponding confirmation from biopsy, surgical pathology or response to treatment.
4. False negative will consist of negative images, but with positive biopsy, surgical pathology or a response to treatment.
5. Sensitivity, specificity, PPV, and NPV of CT and MRI and of ^{11}C -choline PET/CT and MRI will be calculated
6. Performance characteristics between ^{11}C -choline PET/CT and PET/MRI will be compared.

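### Section 5.5 has no unverified class, and step 6 of Section 5.1 requires no follow-up after the report, so missing reference data are scored as test results

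*Combined protocol and SAP*

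**What the plan says.** All sections cited are in the main protocol unless stated otherwise.

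**Section 5.1, step 5** confirms findings by biopsy or surgical pathology where possible, or by treatment response on later imaging. Where pathology cannot be had, "then confirmation will be achieved with ^{11}C -choline PET CT and MRI images obtained 3 months after treatment conclusion". It also has a shortcut: "Unequivocal evidence of metastasis on both conventional imaging and ^{11}C -choline PET will be considered a true positive".

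**Section 5.1, step 6** reads: "Upon conclusion of each imaging protocol, the referring physician will receive written documentation of the results". It continues: "At this time, the patient will be considered off study and no further follow up is required". Section 8.4 places the last routine patient contact at the same moment. After that, Section 8.6 follows only unresolved adverse events.

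**Section 5.5, Data Analysis, items 1 to 4** define the four cells:
- Item 1: a true positive is a positive image that has been confirmed.
- Item 2: "True negatives will consist of negative images".
- Item 3: a false positive is a positive image "without corresponding confirmation from biopsy, surgical pathology or response to treatment".
- Item 4: "False negative will consist of negative images, but with positive biopsy, surgical pathology or a response to treatment".

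There is no class for a result whose reference status was never obtained. Section 6.2 warns: "A negative image does not rule out the presence of recurrent prostate cancer".

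The plan does intend to use later outcomes. Section 5.4.1, item 10 compares the readings with histology or post-treatment imaging. Section 10.2.1 lists histology and treatment results on the case report form and makes the Investigator responsible for its completeness.

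**The concern.** The reference standard for most findings arises after the point at which step 6 stops requiring follow-up. Responsibility for the case report form is assigned. But the available text does not say how outcome records are to be obtained from referring practices, over what period for each patient, or when collection closes. For image-negative patients no reference work-up is planned at all, so item 4 applies only if a positive result happens to come to light.

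The scoring rules then turn this gap into data. Item 3 does not separate a refuted positive from one that nobody checked. Item 2 accepts any negative image. Step 5's rule for findings seen on both modalities is missing from items 1 and 3, so the same patient can be scored differently under the two sections. If that rule is applied, the damage falls mainly on PET-only positives, which decide the comparison with conventional imaging.

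At stake are the accuracy figures in objectives B and E and the comparisons planned in Sections 5.5 and 5.6. A larger sample would not remove this bias.

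**Working it through.** **1. The plan's own figure.** Section 5.5 gives about 66 pairs at alpha 0.05 and 80% power. Take its 4% and 20% as the two discordant cells: their sum is ψ = 0.24 and their difference is d = 0.16. Then n = (1.960 + 0.842)² × (ψ − d²)/d² = 7.849 × 0.2144/0.0256 = 65.7, or 66. This reproduces. The point below does not depend on it.

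**2. Inputs for the illustration.** The 176-patient retrospective series in Section 1.2.1 gives sensitivity 93%, specificity 76%, PPV 91%, NPV 81%, and lesions seen only on PET/CT in 32% of patients. Assumptions:
- These accuracy figures are taken as true.
- The 32% are patient-level and truly metastatic.
- Other PET true positives are also seen on conventional imaging and count as true positives.
- There are no conventional-only lesions.

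The plan gives no confirmation rates, so two more shares are assumed: u, the unconfirmed share of PET-only positives, and v, the share of PET-missed cancers that are confirmed (0 to 1).

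**3. Base table.** Prevalence = PPV(1 − Sp)/[PPV(1 − Sp) + Se(1 − PPV)] = 0.2184/(0.2184 + 0.0837) = 0.723. Per 100 patients: TP 67.23, FN 5.06, FP 6.65, TN 21.06. Conventional TP = 67.23 − 32 = 35.23. True conventional sensitivity = 35.23/72.29 = 48.7%, and the true gap is 93.0 − 48.7 = 44.3 points.

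**4. Apply items 1 to 4.** Unconfirmed PET-only positives, m = 32u, move from TP to FP. Unconfirmed missed cancers, 5.06(1 − v), move from FN to TN.
- PPV = (67.23 − m)/73.88
- Specificity = [21.06 + 5.06(1 − v)]/[21.06 + 5.06(1 − v) + 6.65 + m]
- PET sensitivity = (67.23 − m)/(67.23 − m + 5.06v)
- NPV = [21.06 + 5.06(1 − v)]/26.12
- Conventional sensitivity = 35.23/(67.23 − m + 5.06v)

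| Measure | True | u = 20% (m = 6.4), v = 1 to 0 | u = 50% (m = 16), v = 1 to 0 |
|---|---|---|---|
| PET specificity | 76% | 61.7 to 66.7% | 48.2 to 53.6% |
| PET PPV | 91% | 82.3% | 69.3% |
| PET sensitivity | 93% | 92.3 to 100% | 91.0 to 100% |
| PET NPV | 81% | 80.6 to 100% | 80.6 to 100% |
| Conventional sensitivity | 49% | 53.5 to 57.9% | 62.6 to 68.8% |
| Gap in sensitivity (points) | 44 | 38.8 to 42.1 | 28.4 to 31.2 |

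**5. Direction.** PET sensitivity is overstated when v < 1 − m/67.23, that is v < 0.90 at u = 20% and v < 0.76 at u = 50%. Conventional sensitivity is never understated here, because its denominator cannot exceed 72.29. For very small u the signs can differ. With v = 0, specificity exceeds 76% until m reaches 26.12/0.76 − 32.77 = 1.6 (u = 5%). The gap, (32 − m)/(67.23 − m), exceeds 44.3 points until m is about 4.0 (u about 12.5%); at u = 0 it is 32/67.23 = 47.6 points.

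**6. Other prevalence.** At 50% prevalence (TP 46.5, FN 3.5, FP 12, TN 38; PET-only 32/73.88 × 58.5 = 25.3), true specificity and PPV are 76% and 79.5%. With v = 1 they become 69.0% and 70.8% at u = 20%, and 60.6% and 57.8% at u = 50%.

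**7. Power at 100 pairs.** Multiply both cells by (1 − u) and use z = (√n·d − 1.96√ψ)/√(ψ − d²). At u = 0: (1.600 − 0.960)/0.463 = 1.38, or 92%. At u = 20%: (1.280 − 0.859)/0.419 = 1.00, or 84%. At u = 50%: (0.800 − 0.679)/0.337 = 0.36, or 64%. Enumerating the asymptotic McNemar test gives 94%, 88% and 66%.

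**The case against.** The strongest reply is that step 6 says follow-up is not required, not that records may not be collected. Section 5.4.1 says all patient data will be gathered at the end of the study. Section 10.2.1 makes the Investigator answerable for a case report form that includes histology and treatment results, has the Monitor check it against medical records, and demands attention to missing data. This stands. A reader might infer that nobody is responsible for outcomes or that the plan abandons them; the documents do not support that. What they lack is a retrieval procedure, a per-patient window and a cut-off. The appendix worksheets are not in the available text and might add detail.

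Step 6 refers to each imaging protocol, which could include the repeat scan, and Section 10.3 ends the study only after all scheduled evaluations. Section 5.2 uses the term for the PET/CT and MRI protocols, and Section 7.4 does not limit it to the first scans, so the reading is open. It still gives image-negative patients no reference result and does not provide for pathology obtained after the report.

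The same off-study sentence appears in the expanded access protocol. It does no harm there, because those data are not analyzed.

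It is also fair that the illustration rests on a retrospective series, itself confirmed by pathology in only 41.4% or by conventional imaging, and on assumed u and v. The directions at the u values tabulated follow from the scoring rules under the stated assumptions; the sizes are illustrative. Finally, Section 1.3 names expanded access as the key objective, and that is untouched.

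**Conclusion.** The concern holds. Followed as written, items 2 and 3 of Section 5.5 count missing reference data as results, and Section 5.1 makes missing data likely. In the cases tabulated, PET PPV and specificity fall, NPV rises unless every missed cancer is confirmed, PET sensitivity usually rises, conventional sensitivity rises, and the gap between the two shrinks. At u = 20% and 50%, specificity of 76% becomes 62–67% and 48–54%, PPV of 91% becomes 82% and 69%, and the 44-point gap becomes 39–42 and 28–31 points. These sizes depend on the cited series, on assumed u and v, and on scoring findings seen on both modalities as true positives.

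Two stronger readings do not hold. A reader might infer that the rules manufacture PET superiority; once about one PET-only positive in eight is unconfirmed, they work against it in this example. A reader might also infer that PET sensitivity is 100% by construction. That is a limit reached only if no missed cancer is ever confirmed, and a confirmed lesion seen only on conventional imaging would count against PET.

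Loss of power is secondary: about 92%, 84% and 64% at u = 0, 20% and 50%. Objectives B and E are affected; objective A is not.

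**What to change.** - **Section 5.5, items 2 and 3, changed together.** True negative and false positive each require negative reference information. Every other unconfirmed result is unverified.
- **Reporting.** Give unverified counts by modality and test result, with best-case and worst-case bounds for sensitivity, specificity, PPV and NPV. Any verification-bias correction should condition on both test results and state its assumption that verification does not depend on disease status given those results.
- **Both-modalities rule.** Reconcile step 5 with items 1 and 3.
- **Steps 5 and 6.** Limit the off-study sentence to study imaging, and state whether the repeat scan is a study procedure. Have existing site staff request pathology, treatment and later imaging records up to a fixed cut-off.

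The cost is protocol wording, record requests for about 100 patients, a check that the authorization in Section 3.2 covers them, a few tables and a later database lock. No scan is added beyond the one step 5 already names.

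The bounds will be wide if retrieval is poor. Take u = 20%, half of negatives unverified (TN 10.53, FN 2.53, unverified 13.06) and all false positives refuted:
- Specificity: 10.53/23.58 = 45% to 23.59/30.24 = 78%.
- Sensitivity: 60.83/76.42 = 80% to 67.23/69.76 = 96%.
- PPV: 82% to 91%.
- NPV: 10.53/26.12 = 40% to 23.59/26.12 = 90%.

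If 20% of false positives are also unverified, the upper specificity bound is 23.59/(23.59 + 5.32) = 82%. Such bounds show uncertainty that the present rules hide.
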